### **3.5.1.1. Adverse Events of Special Interest (AESI)**

Certain AEs will be grouped together to support discussion of AEs of Special Interest, these will be reported as clusters using the MedDRA coding as follows with the specific definitions provided in Appendix 2:

- MYELOSUPPRESSION
- HEAMORRHAGE
- INFECTION (Grade  $\geq 3$  and/or serious infection)
- HEPATOTOXICITY (Grade  $\geq 3$  and/or serious hepatotoxicity including all VOD/SOS)
- INFUSION RELATED REACTIONS (including Anaphylaxis): From start of infusion to within 24 hours of end of infusion
- TUMOUR LYSIS SYNDROME
- CARDIAC CONDUCTION

### **3.5.2. Laboratory Data**

Laboratory data will be graded programmatically according to the NCI CTCAE v4.03 severity grade (including low and high values if both are defined for the parameter) for the following safety laboratory parameters:

- Hematology tests: hemoglobin, white blood cells, platelets, neutrophils, lymphocytes.
- Chemistry tests: sodium, potassium, magnesium, glucose, creatinine, total calcium, , albumin, total bilirubin, AST, ALT, alkaline phosphatase (ALP). For laboratory tests that can be either abnormally high or abnormally low, both directions will be computed.
- Coagulation tests: prothrombin time, international normalized ratio (INR), activated partial thromboplastin time, fibrinogen.
- Urinalysis test: protein

The non-CTC graded laboratory tests red blood cells, hematocrit, BUN, LDH, uric acid or urate along with urinalysis tests (pH), will be categorized as below normal limit, within normal limits, and above normal limits. The remaining urinalysis tests (albumin, glucose, blood/hemoglobin, ketones/acetone) will be categorized as negative or positive.

### **3.5.2.1. Time to Recovery of Neutrophils**

For patients who respond, time to recovery of neutrophils for each cycle will be defined as the date of first dose of study treatment to the date that the absolute neutrophils recover to counts of 500/ $\mu$ l after each cycle. During each cycle, the nadir will be calculated. Recovery is not considered to have occurred until after the date of this nadir. If the nadir equals or exceeds the target level of recovery, the date of recovery is defined as the first date after the final dose in the cycle on which the target level was reached. Patients not achieving the target levels of neutrophil recovery are censored at the last laboratory evaluation prior to the next cycle, first follow-up anti-cancer treatment, or death, whichever comes first.

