### 3.4. Baseline Variables

ECG parameters: The last available planned triplicate measurements prior to first dose according to the date (selected from nominal time points of Screening and Cycle 1 Day 1 at 0 hours) will be used as baseline. Triplicate ECGs are collected; therefore the baseline for each ECG measurement is the average of the pre-dose measurements on the selected baseline day. Refer to Section 5.2.8 for further details of derivations concerning ECG parameters.

For safety (including Eastern Cooperative Oncology Group (ECOG) performance status, safety laboratory results, blasts in the bone marrow, blasts in the peripheral blood, immunogenicity) the last assessment performed on or prior to date of the first dose of study treatment will be designated as the baseline assessment. If there are no observations meeting these criteria, then baseline is considered missing. For laboratory data, if there are multiple assessments that meet the baseline definition on the same day without the ability to determine which was truly last, then the worst CTC grade will be considered as the baseline grade.

CD33 expression: CCI (percent positivity CCI [REDACTED] the baseline value will be based on the bone marrow sample that is the last available assessment on or prior to the date of first dose of study treatment. If there is no result available from bone marrow, then a result from a blood sample meeting the same criteria will be used. CCI [REDACTED]

Additionally, percent positivity will be categorized as < 30, 30 - <70,  $\geq$  70; CCI [REDACTED]

The date of first dose (start date) of study treatment is the earliest date of GO dosing.

The date of last dose of study treatment is the latest date of GO dosing.

No windowing will be applied when defining baseline. Although the protocol requires screening assessments to be performed within 28 days prior to first dose; values outside this window will not be excluded when determining baseline assessments.

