### **3.5.2.2. Time to Recovery of Platelets**

For patients who respond, time to recovery of platelets for each cycle will be defined as the date of first dose of study treatment to the date that the platelets recover to counts of 50,000/ $\mu$ l after each cycle. During each cycle, the nadir will be calculated. Recovery is not considered to have occurred until after the date of this nadir. Also, patients are required to be platelet transfusion independent on the date of recovery. Platelet transfusion independence will be defined as no platelet transfusion for at least 7 days prior to the assessment. If the nadir equals or exceeds the target level of recovery, the date of recovery is defined as the first date after the final dose in the cycle on which the target level was reached and the patient was transfusion independent. Patients not achieving the target levels of platelet recovery are censored at the last laboratory evaluation prior to the next cycle, first follow-up anti-cancer treatment, or death, whichever comes first.

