#### 6.6.3.1. Time To Recovery

The analysis of Time to Recovery of Neutrophils and the analysis of Time to Recovery of Platelets will be similar, therefore this section is written generically as “Time to Recovery”.

Time to Recovery for responders will be reported in days and derived as ((recovery date or censoring date) – date of first dose +1) for each cycle (for responders in that cycle).

The summary will include the number of patients recovered to the level of interest and the number of patients not recovered and reported for the safety analysis set.

Time to Recovery will be summarized using the Kaplan-Meier method. The quartiles will be estimated by the Kaplan-Meier method. Confidence intervals (95%) for quartiles will be based on the Brookmeyer-Crowley method.

The estimated survival curves will be displayed graphically (unless there are  $<$  5 responders) with one graph including estimates for the adult and pediatric patients separately. Graphs will describe the number of patients at risk over time.

**Prolonged Cytopenias (Neutrophils and Platelets):** For each cycle, patients with Time to Recovery longer than 42 days will be considered prolonged and summarized for the safety analysis set. The percentage will be based on a denominator that will exclude patients without data to determine the status at Day 42 relative to the cycle start. Thus prolonged cytopenias applies only to patient who are responders in the respective cycle.

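### Two SAP date rules, applied as written, give wrong descriptive safety results: the Cycle 2 recovery clock starts in Cycle 1, and later partial therapy dates become the day after the last GO dose

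*SAP*

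**What the plan says.** **Recovery clock.** SAP 3.5.2.1: "time to recovery of neutrophils for each cycle will be defined as the date of first dose of study treatment to the date" on which neutrophils reach 500/µL. SAP 3.5.2.2: "time to recovery of platelets for each cycle will be defined as the date of first dose of study treatment to the date" on which platelets reach 50,000/µL, with 7 days free of platelet transfusion. SAP 3.4 settles the origin: "The date of first dose (start date) of study treatment is the earliest date of GO dosing". SAP 5.2.4 defines a different date, the cycle start, taken from the first dose on that cycle's own exposure page.

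SAP 6.6.3.1 computes the time as the recovery or censoring date minus "date of first dose +1) for each cycle (for responders in that cycle"), without saying which first dose. It adds that "patients with Time to Recovery longer than 42 days will be considered prolonged", and that the denominator will "exclude patients without data to determine the status at Day 42 relative to the cycle start".

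Two further rules in 3.5.2.1 matter. "If the nadir equals or exceeds the target level of recovery, the date of recovery is defined as the first date" after the cycle's final dose with counts at target. Patients who do not recover are "censored at the last laboratory evaluation prior to the next cycle, first follow-up anti-cancer treatment, or death, whichever comes first".

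**Partial follow-up therapy dates.** SAP 5.3.1.3 compares a partial start date with a reference date, the earlier of last dose + 1 and the therapy end date. It has one branch for a year-only date in an earlier year and one for an earlier month of the same year. Everything else is set to the reference date. SAP 5.2.4 ends the last cycle at the earlier of last dose + 36 and the start of subsequent therapy. SAP 5.2.5 assigns adverse events that start after that to Follow-up.

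**The concern.** The definition sections put the Cycle 2 recovery clock at Cycle 1 Day 1, while the Day 42 rule works from the cycle start. The prolonged-cytopenia rate for Cycle 2 then has its numerator on one clock and its denominator on another. Two programmers following different sections would report different recovery times and rates.

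The imputation rule has no branch for a recorded month or year after the reference date. Such a date falls into the catch-all and is moved to the day after the last GO dose, which contradicts the record. The false date ends the last cycle early. That shortens the window in which the nadir is sought, moves events to Follow-up in the by-cycle adverse event and liver-test tables (SAP 6.6.1 and 6.6.3.2), and can censor unrecovered responders too soon. A truly prolonged cytopenia can then drop out of a safety rate.

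**Working it through.** The plan gives no figure for this point, so the written rules were applied directly.

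**1. Recovery clock**

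Let S be the study day of Cycle 2 Day 1 and R the Cycle 2 day of recovery. Recovery falls on study day S + R − 1, so

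- time as written = (S − 1) + R;
- time from cycle start = R;
- not prolonged as written needs (S − 1) + R ≤ 42, that is R ≤ 43 − S.

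Protocol 6.2.1 allows Cycle 2 to start up to 42 days after Cycle 1 Day 7, so S can reach 7 + 42 = 49. SAP 6.5.3 has reporting bands for Days 35–42 and 43–49. For illustration R is 23 or 20, the median recovery times for neutrophils and platelets that Protocol 1.2.2.4 cites from an earlier Phase 2 study of the fractionated regimen. Their use for Cycle 2 is an assumption.

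| S | Days added | Latest R not prolonged | As written, R = 23 | As written, R = 20 |
|---|---|---|---|---|
| 22 | 21 | 21 | 44 | 41 |
| 28 | 27 | 15 | 50 | 47 |
| 35 | 34 | 8 | 57 | 54 |
| 42 | 41 | 1 | 64 | 61 |
| 43 | 42 | none (43 − 43 = 0) | 65 | 62 |
| 49 | 48 | none | 71 | 68 |

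Counted from the cycle start, these times are 23 and 20 days and none is prolonged.

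Now take a patient whose neutrophils never fall below 500/µL in Cycle 2. Recovery is then the first date after the last dose with counts at target. If that is the scheduled Day 10 count and S = 34, the time as written is 33 + 10 = 43 days, against 10 from cycle start. The same holds for every start from Day 34 on.

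The number of Cycle 2 responders is not given. If it were 3, 5 or 10 (assumed), one misclassified patient would move the rate by 33, 20 or 10 percentage points.

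**2. Partial therapy date**

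Example: first dose 1 May 2020, last dose 7 May, therapy start recorded as August 2020 and ongoing.

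- The reference date is 8 May (no end date). August is neither an earlier year nor an earlier month, so the catch-all gives 8 May.
- From 8 May to 1 August is 85 days, and to 31 August 115 days. The imputed date is 85 to 115 days early.
- The last cycle should stop at 7 May + 36 = 12 June. As written it stops on 8 May, 35 days sooner.
- The scheduled Day 10, 15, 21 and EOT assessments (10, 15 and 21 May, 12 June) all fall outside it.
- A responder still unrecovered at an EOT count on 12 June should be censored at cycle day 43 and counted as prolonged. As written, the last count before 8 May is that of 7 May (day 7). Day 42 status is then unknown and the patient leaves the denominator.

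Year-only dates fail in the same way: after a last dose on 20 December 2019, a therapy year of 2020 becomes 21 December 2019. SAP 5.3.1.5 does not help, because it covers only other dates.

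**The case against.** **Intent is clear enough.** The definitions say each cycle, and 6.6.3.1 refers to responders in that cycle and to the cycle start. A careful programmer would probably use the cycle's own first dose. That is likely, but the phrase in 3.5.2.1 and 3.5.2.2 is a defined term that points to Cycle 1 Day 1, so the contradiction stands and should not be left to judgement.

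**The reach is small.** This is fair. Part 1 touches only patients who receive the optional second cycle and respond in it; the Cycle 1 clock is correct. For recovery censoring, part 2 needs a later partial date in a responder who has not recovered. Marrow is assessed at count recovery or by 36 days after the last dose (SAP 3.2.3), at the same count levels as the recovery targets, so such responders are few. They are mainly CRi patients, because CR requires counts above both targets. A CR patient can still fail the platelet transfusion condition. The by-cycle tables are exposed more widely, since any patient with a later partial date is affected there.

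**The example is tight.** The EOT window is ±2 days. A last count on 11 June gives 42 days, which is not over 42, and one on 10 June leaves Day 42 unknown even with the right therapy date. The example shows what can happen, not what must.

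**The repair is partial.** This is also true; the remaining cases are given with the fix.

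**Conclusion.** The concern holds on both parts, and both rules should be corrected before the tables are programmed.

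For Cycle 2, the literal clock adds S − 1 days to every recovery time and makes every responder prolonged for starts from Day 43. The bands in SAP 6.5.3 and the protocol's own limit show that such starts are expected. A per-cycle origin was probably intended, so this is a contradiction between sections rather than a deliberate choice.

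For partial dates, the rule contradicts the record whenever the known month or year is later than that of the reference date. In the example the error is 85 to 115 days and the last cycle loses 35 days. Partial dates in the same month or year as the reference date are not contradicted.

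The number of Cycle 2 responders and of partial dates cannot be known from the documents, so the effect on the reported rates is unquantified and may be small. The primary QTcF analysis is unaffected. So are the overall adverse event summaries and the laboratory shift tables, because the on-treatment period in SAP 3.5 runs to the end of follow-up.

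**What to change.** **SAP 3.5.2.1, 3.5.2.2 and 6.6.3.1:** replace the first dose of study treatment (or first dose) with the cycle start date defined in 5.2.4, the first GO dose in that cycle. Recovery on cycle day 23 of Cycle 2 then counts as 23 days whatever the start day.

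**SAP 5.3.1.3:** keep the existing branches and the catch-all, and add two branches before the catch-all:

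- year and month known and later than those of the reference date: impute the first day of that month;
- only the year known and later: impute 1 January of that year.

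In both, never impute later than the therapy end date as 5.3.1.3 sets it. This matches the start-date convention in 5.3.1.5. In the example, August 2020 becomes 1 August and the last cycle stops on 12 June.

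The cost is a few lines of text and programming. The imputed date is still the earliest one compatible with the record, so it can be up to 30 days early with a known month, or about a year early with only the year. Some early censoring remains. A year-only 2020 after a last dose on 7 May 2020 still becomes 8 May. June 2020 becomes 1 June, which is cycle day 32 and still before Day 42. SAP 5.3.1 already requires imputed dates to be marked in listings, so these cases can be identified there.

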### **5.2.4. Definition of Cycle and Cycle Day**

For Cycle 1 and Cycle 2 the actual start date for each patient will be determined from the first start date of dosing from the respective CRF exposure page with a dose recorded.

If Cycle 2 is administered, then the actual stop date for Cycle 1 will be calculated as the start date of Cycle 2 minus one day.

For the last Cycle, actual stop date will be calculated as the minimum of the last dose + 36 and the start date of subsequent anticancer therapy.

The cycle day will be calculated as Cycle day = Date of the assessment/event – cycle start date + 1.

The cycle day will be displayed in all relevant data listings.

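### The time-to-recovery rule applies its after-the-last-dose condition only when the cycle nadir is at or above target, so a low count on a dosing day can date recovery before the post-treatment trough, and a late dip can cancel a recovery

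*SAP*

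**What the plan says.** SAP 3.5.2.1 ends the neutrophil interval on "the date that the absolute neutrophils recover to counts of 500" per µL. It then adds two conditions.

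- One lowest count is found per cycle, and the SAP states: "Recovery is not considered to have occurred until after the date of this nadir".
- Where that lowest value already meets the target, a different rule applies: "the date of recovery is defined as the first date after the final dose in the cycle on which the target level was reached".

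The requirement that recovery follow the last dose stands only in the second condition. SAP 3.5.2.2 has the same structure for platelets at 50,000/µL and also requires 7 days free of platelet transfusion.

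SAP 5.2.4 sets the window. "The cycle day will be calculated as Cycle day = Date of the assessment/event – cycle start date + 1", so the first-dose date is Day 1 of the cycle. If there is a Cycle 2, "the actual stop date for Cycle 1 will be calculated as the start date of Cycle 2 minus one day". A patient's final cycle instead closes 36 days after its last dose, or when new anticancer treatment begins if that is sooner. SAP 5.2.5 assigns laboratory results to cycles. Protocol Table 1, note 11, has the Day 1, 4 and 7 samples drawn before dosing.

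The result is used again in SAP 6.6.3.1, where "patients with Time to Recovery longer than 42 days will be considered prolonged".

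**The concern.** A time-to-recovery endpoint should measure the return of counts after the trough that treatment produces. A nadir taken over the whole cycle need not be that trough.

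- **Early low.** Patients enter with active leukaemia. Protocol 4.1 sets no minimum neutrophil or platelet count, and Protocol 5.4.3 does not require haematologic recovery before the Day 4 and Day 7 doses. A dosing-day count may therefore be the lowest of the cycle, and the next count at target then ends the clock.
- **Late low.** Counts continue to the end-of-treatment visit, weekly once remission status is known (Protocol Table 1, note 12). The nadir search does not stop at first recovery, so a later and lower value resets it.
- **Ties.** If the lowest value occurs on several dates, the SAP does not say which date is the nadir.

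The figures at stake are the Kaplan-Meier recovery times and the prolonged-cytopenia percentage, both in responders only. Protocol 1.2.2.4 reports median recovery of 23 days (neutrophils) and 20 days (platelets) for the earlier fractionated-regimen study, against 40.5 and 51 days in the original-regimen studies. Readers are likely to set this trial's results beside those.

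**Working it through.** The documents give no figure that depends on this rule, so there is nothing to reproduce. The check applies the rule literally to constructed neutrophil series. The counts are assumptions chosen to show the mechanism.

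**Inputs from the documents.** Target 500/µL (SAP 3.5.2.1). Doses on Days 1, 4 and 7. End of the last cycle = 7 + 36 = Day 43 (SAP 5.2.4). Time = recovery or censoring date − first-dose date + 1 (SAP 6.6.3.1), so time equals the day number in Cycle 1.

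**Rules compared.**
- Literal rule: let m be the lowest count of the cycle. If m < 500, recovery is the first count ≥ 500 after the date of m. If m ≥ 500, it is the first count ≥ 500 after the last dose.
- Repair: use only counts after Day 7. Recovery is the first count ≥ 500 after the first post-dose count below 500. If no post-dose count is below 500, it is the first count ≥ 500 after Day 7.

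| Series (counts/µL; D = day) | Nadir date | Literal rule | Repair |
|---|---|---|---|
| Ordinary single trough: D15 100, D24 600 | D15 | Day 24 | Day 24 |
| Low on Day 1: D1 50, D4 600, D7 400, D15 100, D24 550 | D1 | Day 4 | Day 24 |
| Same, Day 1 count left out | D15 | Day 24 | Day 24 |
| Low on Day 4, no Day 1 count used: D4 50, D7 600, D15 100, D24 550 | D4 | Day 7 | Day 24 |
| Low on Day 4, never below 500 afterwards: D4 50, D7 600, D10 700 | D4 | Day 7 | Day 10 |
| Ties at 0 on D1, D10, D15; D4 600, D24 600 | D1 or D15 | Day 4 or Day 24 | Day 24 |
| Late dip: D15 100, D24 600, D28 1300, D42 50, D43 60 | D42 | not recovered, censored Day 43 | Day 24 |
| Late dip with rebound: D15 100, D24 600, D35 90, D42 700 | D35 | Day 42 | Day 24 |
| Late dip above the first trough: D15 100, D24 600, D42 120 | D15 | Day 24 | Day 24 |

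The early error needs a below-target dosing-day count that is the lowest or tied-lowest of the cycle, followed by a count at target by Day 7. The late error needs a dip below the first trough, or equal to it if the last tied date is used.

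**Scale.** If the response rate in the earlier fractionated-regimen study (19 of 57, Protocol 1.2.2.4) held in 50 adults, there would be 50 × 19/57 = 16.7, about 17 responders. One patient is then 1/17 = 5.9 percentage points of the prolonged-cytopenia figure, and more if patients without Day 42 status leave the denominator (SAP 6.6.3.1). Misdating from Day 24 to Day 4 moves that figure by zero, since both lie below 42. The late dip censored at Day 43 can move it; the one that recovers on Day 42 does not.

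**Median.** As an illustration, take 17 lognormal recovery times with median 23 days and log-SD 0.25 (the spread is an assumption with no source in the documents). Setting 0, 1, 2 or 3 of them to Day 4 or 7 gives an average sample median of 23.1, 22.6, 22.2 (22.15 unrounded) or 21.6 days. Three misdated patients cost about 1.5 days.

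**The case against.** **The Day 1 count may be meant as baseline only.** SAP 3.4 treats the last laboratory value on or before the first-dose date as baseline, and SAP 6.6.3 leaves baseline values out when taking the worst on-treatment grade. Read across, the Day 4 misdating from a Day 1 low disappears. This partly stands: the exclusion is written for toxicity grading, 3.5.2.1 does not repeat it, and 5.2.4 places Day 1 in the cycle by date. The Day 4 low remains in either case.

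**The opening sentence of 3.5.2.1 places recovery after each cycle.** If that means after the cycle's dosing, no early date is possible. This may be the intention, but it is not what 5.2.4 defines. With the cycle running to Day 43, the literal reading puts recovery beyond Day 43, which conflicts with censoring before the next cycle and with the 42-day summary.

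**A count that later collapses below the original trough was arguably not a recovery.** That is a defensible choice. Such dips should also be rare in responders, whose cycle ends when new therapy starts, and nothing can fall below a trough of zero. The late-dip part is therefore the weaker one.

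**Platelets are better protected.** The 7-day transfusion-free condition rules out Day 4 or Day 7 for anyone transfused around Day 1. It does not protect an untransfused patient, and it does not stop a late dip from resetting the nadir.

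**A stronger reading is tempting.** A reader might infer that the trial's account of marrow toxicity is unreliable, or that every misdated patient shifts the prolonged-cytopenia percentage. The documents support neither. The SAP also reports myelosuppression as an event of special interest, haematology grade shifts and transfusion days, and the early error generally leaves the percentage unchanged.

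**Conclusion.** The rule is wrong as written, but the consequence is small. The final-dose condition is missing from the branch where the nadir is below target, so a low count on Day 4 (or on Day 1, if that sample is in the cycle) can date recovery on or before the last GO dose. A late dip below the first trough can erase a recovery, though less often, and how to treat that is partly a matter of choice. With tied nadirs the answer is left to the programmer.

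How many patients are affected cannot be derived from the documents; few is the reasonable expectation. The median would move by about half a day per early-misdated responder under the assumed spread. The prolonged-cytopenia percentage moves mainly through the late dip, by about 6 points per patient if there are about 17 responders. The early error would matter there only if the true recovery lay beyond Day 42. The QTc primary analysis, response and survival are unaffected.

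**What to change.** In SAP 3.5.2.1 and 3.5.2.2, for both branches:

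1. Restrict the nadir and recovery search to counts dated after the final dose in the cycle.
2. Define recovery as the first count at or above target after the first post-dose count below target. For platelets, the patient must also be transfusion-independent on that date.
3. If no post-dose count is below target, define recovery as the first count at or above target after the final dose, with the same platelet condition. Keeping the present wording for these patients would not do: Day 4 at 50, Day 7 at 600 and later counts at or above 500 would still give Day 7.
4. Once recovery is dated, do not let later dips cancel it; report them separately.

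The date then no longer depends on which tied nadir is chosen.

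There is one trade-off. A brief rise between the first low and the trough would count as recovery: with D10 200, D15 510, D17 100, D24 600 and D28 1200, the repair gives Day 15. Requiring two consecutive counts at target would give Day 24. Such confirmation is optional; once counts are weekly it can take up to a week.

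The cost is SAP wording and programming. No new data are needed.
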